### Final Visit (6-month Follow-up Visit)

The window for the final visit will be three months after the 3-month follow-up date ( $\pm 15$  days). The following study procedures are performed at this visit:

- Medical history form
- Anthropometric measurements

- Venipuncture, specimen collecting, and specimen processing
- Urine pregnancy screen (only post-menarchial girls require urine pregnancy screen). Subjects with a positive pregnancy screen will not undergo a DXA scan but can complete the remaining study procedures if they are willing.
- Activity survey
- Nutritional survey
- Vitamin D and Sunlight Exposure Questionnaire
- DSM II Colormeter Measurement: Will be measured at similar body sites as the baseline testing
- Vascular function testing (pulse wave velocity, pulse wave analysis, and brachial flow mediated dilation, and blood pressure measurements)
- DXA scan
- Medication adherence assessment
  - Collect medication calendar
  - Read MEMs cap and obtain Patient Adherence Report

## **7. SAFETY ASSESSMENTS**

### **7.1 Specification of Safety Parameter**

- Serum calcium levels will be monitored for participant safety. Serum calcium  $>10.8$  mg/dL in 10- to 14-year-old children and  $>10.2$  mg/dL in  $\geq 15$ -year-old children will prompt further evaluation. An elevated serum calcium level will be repeated and if still abnormal, study medication will be discontinued. Children who discontinued study medication due to hypercalcemia will have serum 25(OH)D measured to rule out vitamin D toxicity (levels  $\geq 100$  ng/mL) and will be referred to a pediatric endocrinologist for further evaluation and management. Children with hypercalcemia and normal serum 25(OH)D levels ( $<100$  ng/mL) will be also be referred for further evaluation to their primary care provider and a pediatric endocrinologist to rule out other unusual causes of hypercalcemia (chronic granulomatous disorders, primary hyperparathyroidism, familial hypocalciuric hypercalcemia).
- Significant fasting hyperglycemia (fasting blood glucose  $>125$  mg/dL) during enrollment visit will disqualify subject from enrolling in the study.
- Post-menarchial girls that test positive during pregnancy screen at the enrollment visit will be excluded. Positive screens in the final visit will disqualify subject from getting a DXA scan but will not exclude subject from completing the study.
- At the 3-month follow-up and the final visit, the MEMS cap data will be downloaded to assess adherence.

### **7.2 Methods and Timing for Assessing, Recording, and Analyzing Safety Parameters**

Serum calcium will be measured at the screening visit and only children with normal calcium results for age will be eligible to enter the study. Upon enrollment, serum calcium will be monitored for safety at the 3-month and 6-month follow-up visits, and children found to have elevated serum calcium ( $>10.8$  mg/dL in 10- to 14-year-old children and  $>10.2$  mg/dL in  $\geq 15$ -year-old children) will be further managed as stated above in section 7.1.

### 7.3 Adverse Events and Serious Adverse Events

An adverse event is any unintended medical occurrence (symptom, diagnosis, sign, abnormal laboratory finding, or missed study procedure) that occurs during the study that was not present at baseline.

- Any medical condition present at the time of enrollment is considered baseline, and not reported as an adverse event.
- If the severity of a pre-existing medical condition worsens at any time during the study participation, it will be considered an adverse event.
- All adverse events will be assessed by the Principal Investigator to determine the severity of the event (mild, moderate, severe, life-threatening) and whether the event is related to the study product or study intervention
- All AEs will be recorded in the eCRF in the study database. The event description, date of onset and study clinician's assessment of severity and relationship to study product, date of resolution and outcome will be recorded. To elicit any adverse event, the parent will be prompted at each encounter to report any change in their child since the last contact.

A serious adverse event (SAE) is any unintended medical occurrence in which the patient outcome is death or life-threatening hospitalization, disability, or incapacity.

- In the event of an SAE, the SAE eCRF must be completed by the research coordinator and the details of the relevant SAE should be notified to the PI ([name]) immediately. The event description, date of onset and study clinician's assessment of severity and relationship to study product, and outcome of event will be recorded.
- SAEs will be logged in the electronic database and will be periodically monitored by the study statistician.

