### 7.4 Reporting Procedures

- All AEs will be reported to the Data and Safety Monitoring Board annually.
- Unanticipated protocol-related problems will be notified by the PI ([name]) to the IRB as and when they occur
- All SAEs must be reported by the research staff to [name], the study principal investigator, immediately. Principal investigator will report SAEs to the University of Pittsburgh Institutional Review Board (IRB) according to the local IRB requirements. SAEs related to the research intervention will be notified by the PI ([name]) to the IRB within 24 hrs. AEs of moderate severity related to the research intervention will be notified by the PI ([name]) to the IRB within 5 days.

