### 9.2 Sample Size and Randomization

Our sample size estimates are based on showing a relative improvement in baseline brachial artery flow mediated vasodilation (FMD, %) of at least 25% in children receiving each of the higher doses of vitamin D3 (1000 IU and 2000 IU) compared with no improvement in the 600 IU group after six months of treatment. We assumed the baseline FMD was ~6.5% based on previous studies in overweight children similar to our projected population. A sample size of 56 in each treatment group at the end of the trial would have 84% power (two-sided two-sample comparison of means,  $\alpha=0.025$ ) to detect this clinically important difference of 25% relative improvement (absolute improvement=25%\*6.5%≈1.6%) assuming a standard deviation of 2.6% (conservative estimates based on published literature). To provide for a projected drop-out rate of 25% by the end of the trial, we propose to recruit 225 children into the trial. We have over 90% power to detect a dose-response effect by testing for linear trend assuming a 0%, 20%, and 30% improvement in vascular health among children receiving 600 IU, 1000 IU, and 2000 IU, respectively.

Our original sample size of n=252 was based on 90% power and 20% attrition to allow for subgroup analyses by race. In December of 2015, the PI and funder decided to re-evaluate the targeted sample size due to slower than expected recruitment. Accordingly, with approval from NHLBI, our accrual target was revised from 252 participants to 229 participants based on projected enrollment and power of at least 80% to detect the original effect size with 25%-30% attrition. The lower sample size of n=225 would still allow for detection of clinically significant effect of vitamin D supplementation. However, the proportion of African Americans in the recruited sample was much larger than anticipated; the small number of Caucasian subjects in the cohort precludes doing race-stratified analysis. For the secondary outcomes, we have 89% power to detect effect sizes of 0.61 or greater without adjustment for multiplicity.

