### **9.3 Interim analyses and Data and Safety Monitoring Plan**

No interim efficacy analysis has been planned. [name] will work with [name] to prepare a DSMB report addressing specific concerns that she anticipates the DSMB may have regarding the conduct of the study. This will be distributed to DSMB members along with the Open Session report. Likewise, [name] report for the Closed Session will usually contain an assessment of the progress of the trial, including recommendations as to whether it should be terminated or modified. Interim data reports will generally include the following types of information, although only the Closed Session data reports will include comparisons by treatment group:

- Monthly and cumulative accrual compared with targets
- Baseline characteristics, overall and by treatment group
- Completeness and quality of data collection forms
- Status of enrolled participants, overall and by treatment group
- Participants' off-protocol treatments
- Compliance with eligibility criteria and other protocol requirements
- Subject adherence to the treatment regimen, overall and by treatment group
- Individual SAEs by subject ID number and a table of event-specific cumulative rates, overall and by treatment group

[name] will work to ensure that all the information presented at the DSMB meetings remains confidential. Each report will be marked as such. At the end of each DSMB meeting, all reports will be collected and destroyed. At the end of the meeting, the DSMB will make recommendations regarding the continuation of the trial. [name] will implement the DSMB recommendations. [name] will also submit the DSMB recommendations to the IRB.

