### Protocol Deviations

Any protocol deviations recognized by study staff will be communicated to [name] (PI). The PI will determine if the IRB needs to be immediately apprised of the deviation or can be informed at the next renewal. This deviation will be documented in the "As Needed" forms in the CRHC database. The protocol deviations and the course of actions taken to address the deviations will be discussed in the next DSMB meeting.

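### Section 7.3 counts a missed study procedure as an adverse event, so any overall adverse event count would mix attendance with harm

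*Combined protocol and SAP*

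**What the plan says.** Section 7.3 opens with the definition: "An adverse event is any unintended medical occurrence (symptom, diagnosis, sign, abnormal laboratory finding, or missed study procedure". The list thus ends with "abnormal laboratory finding, or missed study procedure", and the second of these is the item at issue. The event must also occur during the study and not have been present at baseline. The same section has the principal investigator grade every adverse event from mild to life-threatening and judge "whether the event is related to the study product or study intervention". For each record, "The event description, date of onset and study clinician's assessment of severity and relationship to study product, date of resolution and outcome will be recorded".

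Section 7.4 then states: "All AEs will be reported to the Data and Safety Monitoring Board annually". Section 7.6 has the board weigh adverse events, as the risk, against benefit.

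Two other routes already deal with attendance:

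- Section 10.3, under Protocol Deviations, has deviations logged on their own form and adds: "The protocol deviations and the course of actions taken to address the deviations will be discussed in the next DSMB meeting".
- Section 9.5, under Missing Data, classes children who leave as dropouts, monitored with reasons. It does not call them adverse events.

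The event item in the DSMB reports that is split by arm (Section 9.3, repeated in the Section 10.3 metrics) is: "Individual SAEs by subject ID number and a table of event-specific cumulative rates, overall and by treatment group".

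**The concern.** The last item in the Section 7.3 list does not fit the term it is meant to illustrate. The other items are clinical findings, whereas a missed procedure is an event of trial conduct. Neither the severity scale nor the relatedness question has a sensible answer for a scan that was not done, and the resolution date that Section 7.5 asks the family to supply has no clear meaning.

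Two coordinators could reasonably code the same missed scan differently, one as an adverse event and one only as a deviation. If it is coded as both, the board sees it twice under two labels.

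What is at stake is the meaning of an overall adverse event count. Attendance would enter the risk side of the board's assessment, and a published proportion of children with any adverse event would be partly a measure of retention. Nothing in the plan says that missed procedures are to be tabulated apart.

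**Working it through.** **Inputs from the documents**

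- Accrual target N = 229, 1:1:1 allocation (Sections 9.1 and 9.2), so 229/3 ≈ 76 per arm.
- Attrition: Section 9.2 says "To provide for a projected drop-out rate of 25% by the end of the trial", and later 25-30% for the revised target. Section 9.5, Missing Data, expects less than 20%.
- Adverse event rate: none is given, and no power is stated for a safety comparison.

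**The plan's own attrition arithmetic.** 56 per arm × 3 = 168, and 168/(1 − 0.25) = 224, against the 225 stated. It reproduces to within one child.

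**Children who could be added.** If every child lost to follow-up is counted as having an adverse event, the number is N × attrition:

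| Attrition | Children of 229 | Per arm |
|---|---|---|
| 20% (upper limit in 9.5) | 45.8, about 46 | about 15 |
| 25% | 57.25, about 57 | about 19 |
| 30% | 68.7, about 69 | about 23 |

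These are the most that losses to follow-up could add, because some of these children would also have a genuine adverse event and be counted anyway.

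**Effect on a crude any-event proportion (illustration).** Let p be the true proportion with a medical adverse event and m the proportion with a missed procedure, assumed independent of p. The observed proportion is q = p + (1 − p)m. With the same m in both arms, a true difference shrinks by the factor (1 − m).

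The share of flagged children who have only a missed procedure is (1 − p)m/q. At m = 0.25:

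| Assumed p | 5% | 10% | 20% | 40% |
|---|---|---|---|---|
| Share with only a missed procedure | 83% | 69% | 50% | 27% |

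Power for a two-arm comparison, 76 per arm, two-sided α = 0.05, normal approximation, with all true rates assumed:

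| Assumed true rates | Not counted | m = 20% | m = 25% | m = 30% |
|---|---|---|---|---|
| 10% v 20% | 41% | 18% | 16% | 14% |
| 10% v 30% | 88% | 54% | 47% | 41% |
| 20% v 40% | 77% | 51% | 46% | 41% |

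For example, with 10% v 30% and m = 25%, the observed rates are 0.10 + 0.90 × 0.25 = 32.5% and 0.30 + 0.70 × 0.25 = 47.5%. A 20-point difference becomes 15 points.

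**Unequal attendance (illustration).** With an equal true rate of 10% and missed-procedure rates of 20% and 30%, the observed rates are 0.10 + 0.90 × 0.20 = 28% and 0.10 + 0.90 × 0.30 = 37%. This is an apparent difference of 9 points with no difference in harm.

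**The case against.** A reader might infer that expected dropout would swamp the safety comparison between doses. The documents do not support that, for four reasons.

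- **No such comparison is planned.** Section 9.5 has no test of adverse event rates between doses, and Section 7.4 asks only for annual reporting.
- **The planned safety outputs are unaffected.** The by-arm event item names SAEs, whose definition a missed visit does not meet. If the event-specific table were read to cover all adverse events, a missed procedure would be its own row and the clinical rows would not change. Calcium monitoring has its own numeric thresholds.
- **Records can be separated later.** Each carries a description and a relatedness judgement, so no clinical information is lost.
- **The size cannot be derived.** Without an adverse event rate, the share of flagged children with only a missed procedure could be anything from 27% to 83% over the rates shown at 25% loss. The power figures are illustrations, and the 10% v 20% case has only 41% power before any missed procedure is counted. Nothing in the documents indicates that attendance will differ by arm.

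It can also be argued that the head term, a medical occurrence, excludes a child who simply stops attending, and that moving these events to the deviation log is only a filing choice because the board sees deviations too.

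The four points stand and limit the claim. The last two do not remove it. If the head term excludes non-medical absence, the listed item contradicts it and staff must choose which to follow. Filing matters because the board reads adverse events as risk and deviations as conduct. Later separation is possible, but the plan does not call for it.

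**Conclusion.** The point holds as a minor defect in a definition. Following Section 7.3 as written puts attendance into any overall adverse event count. If every lost child were counted, that means up to about 46 children at 20% attrition, or 57 to 69 of 229 (19 to 23 per arm) at 25-30%. A crude any-event comparison between doses could be diluted, or biased if attendance differed by arm.

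This rests on three assumptions: that staff apply the listed item literally, that losses to follow-up stand in for missed procedures, and that someone forms a pooled any-event count. The degree of dilution also depends on an adverse event rate that the documents do not state. The primary endpoint, the sample size, the SAE table by arm, event-specific rates and calcium monitoring are not touched.

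**What to change.** Delete the last item of the list in Section 7.3 (the words 'or missed study procedure') and record missed procedures as protocol deviations under Section 10.3. Where such events have already been entered as adverse events, identify them from the event description, tabulate them separately and leave them out of adverse event counts.

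The cost is four words and a minor re-sorting of existing records. No endpoint, analysis or sample size changes, and there are fewer events to grade and follow to resolution.

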#### **4.3 Study Enrollment Procedures**

Participants will be recruited from the Primary Care Center of CHP Oakland or at affiliated PittNet offices. In addition to the two recruitment locations, participants may also be recruited through various community outreach programs. The study will also be advertised through the University of Pittsburgh Pitt+Me database to strengthen our recruitment effort.

Potential participants among children attending the CHP Oakland Primary Care Center will be screened for eligibility by reviewing their EPIC electronic medical records. Subjects who are not excluded during the preliminary EPIC chart review will be approached for screening. Reasons for inclusion and exclusion will be electronically documented on a screening form in the study-specific electronic database administered by the University of Pittsburgh Center for Research on Health Care (CRHC).

Written informed consent from a biological or legally-adoptive parent and participants' assent, will be obtained prior to enrollment (both screening and enrollment) of 10- to 17-year-old children. Participants who are 18 years of age can consent for themselves for both screening and enrollment. Legal guardians will have to provide documentation of guardianship from relevant agencies and/or courts.

Participants found to be vitamin D-deficient during screening, and thus eligible for study enrollment, will be randomized to one of three vitamin D supplementation doses (600 IU, 1000 IU, or 2000 IU). The randomization codes will be assigned electronically through the CRHC study database using a block randomization scheme set forth by the study statistician prior to the onset of the study. Both participants and study investigators will be blinded to the assigned supplementation dose throughout the trial.

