## Screening Evaluation

### **Consenting Procedure**

Written informed consent will be obtained separately for screening and for enrollment, at the respective study visits. The parent or medical legal guardian of the child (as defined by state law) will be given a copy of the informed consent and will be provided an opportunity to read the consent in its entirety. For a legal guardian to consent on behalf of a child to participate in research, the guardian must present a copy of the appropriate legal document proving guardianship under state law before signing the consent document. A copy of the guardianship document will be included in the research subject's chart.

The consent form given at the screening visit will describe the procedures that will take place only during the screening visit. The consent form given at the enrollment visit will detail all procedures to be performed at each study visit. Participants must give their assent and only biological parents, or legally-recognized guardians, may provide consent.

Only trained study coordinators and the principal investigator may obtain informed consent from participants. Person obtaining consent will review all aspects of the consent and allow the parent or legal guardian the opportunity to ask questions. The following points will be explained to the parent(s) or legal guardian(s) at the time of consent:

- The study involves research
- The purpose, background and rationale of the study
- Study involves taking vitamin D supplementation (Vitamin D3 600 IU vs. 1000 IU vs. 2000 IU once daily for six months) which has been masked and randomly assigned
- The responsibility of the parent and the participant
- All reasonably foreseeable risks or inconveniences associated with all the expected study procedures (i.e. vascular function tests, DXA scan, blood draw, skin color estimation, completion of physical activity, diet and sun exposure surveys)
- Potential risk of hypervitaminosis D (vitamin D poisoning) and its symptoms
- The expected benefits of the study
- The participation in this study is voluntary and that the parent or subject may refuse to participate or withdraw from the study at any time without penalty or loss of benefits to which he/she may be entitled
- The accessibility of the records to the regulatory authority(ies), monitor(s), auditor(s), or other appropriate reviewers
- Maintenance of confidentiality of the patient record

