## **Screening**

The following procedures are performed to determine a subject's eligibility:

- *Age Calculation:* To enter the study children should have completed their 10th birthday and not have had their 19th birthday. 18-year-old children are eligible to enroll until the day before their 19th birthday.
- *BMI Calculation:* Height will be measured three times in centimeter (cm) to the nearest 0.1-cm and averaged to determine the participant's height in centimeter. Weight will be measured three times in kilogram (kg) to the nearest 0.1-kg and averaged to determine the participant's weight in kilogram. BMI will be calculated using the following formula:

$$[\text{Weight in kilogram}]/[\text{Height in meter}]^2$$

BMI can also be calculated using metric measurements of height (in cm) and weight (in kg) through NHLBI online BMI calculator available at:

<http://nhlbisupport.com/bmi/bminojs.htm>

- *Medical History Form:* Captures anthropometrics, demographic data (age, sex, race, and ethnicity), level of education, smoking status, current medications, and type of medical insurance.
- *Contact Form:* To be completed by parent unless subject is 18 years of age
- *Vitamin D and Sunlight Exposure Questionnaire:* To be completed by parents unless subject is 18 years of age
- *Waist Circumference Measurement:* Waist circumference will be measured three times, using a non-stretch tape measure, at the mid-point between the lowest rib and the iliac crest at minimal respiration while standing. The respective waist circumference measurements will be measured to the nearest 0.1 cm and averaged.
- *Fitzpatrick Sun-reactive Skin Type estimation:* Sun-reactive skin type estimate will be made by the parent unless the subject is 18 years of age
- *DSM II Colormeter Measurement:* Study staff will normalize the dermatophotopspectrometer on the calibration plate and obtain three readings from the forehead, back of the hand, and inner upper arm. The measurements obtained at each site will be averaged to estimate the melanin index at the respective sites.
- *Venipuncture, Specimen Collection, and Specimen Processing:*

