### 7.5 Follow-up for Adverse Events

- Follow-up of a non-serious adverse event of mild or moderate severity will end when the study reporting period ends [i.e., 6-month follow-up visit (final study visit)]. Study staff will keep apprised of subject's adverse event until the parent/subject provides a date of resolution for the AE; resolution date will be documented in the CRHC database.

- Follow-up for a non-serious adverse event of severe nature will be the following:
  - At the time of the event, the investigator will provide appropriate treatment or follow up, including communicating the event to the child's primary care provider and/or providing a referral to a specialist.
  - The staff will place a follow up phone call to the parent, regardless of the study reporting period, to assure that the child is improving or that the family has connected with the suggested referral. Study staff will keep apprised of subject's adverse event until the parent/subject provides a date of resolution for the AE; resolution date will be documented in the CRHC database.

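### Section 7.3 prompts only the parent for adverse events; no direct question to the participant is specified, even at age 18, so symptoms unknown to the parent may be under-ascertained.

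*Combined protocol and SAP*

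**What the plan says.** The elicitation rule in section 7.3 (Adverse Events and Serious Adverse Events) reads: "To elicit any adverse event, the parent will be prompted at each encounter to report any change in their child since the last contact". The same section makes symptoms part of the definition: "An adverse event is any unintended medical occurrence (symptom, diagnosis, sign, abnormal laboratory finding, or missed study procedure"). It also sets a general recording rule: "All AEs will be recorded in the eCRF in the study database".

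The age range includes legal adults. Under Screening in section 6.2, "18-year-old children are eligible to enroll until the day before their" 19th birthday. Section 4.3 adds: "Participants who are 18 years of age can consent for themselves for both screening and enrollment". Section 11.2 and the consenting procedure in 6.2 say the same.

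Section 7.5 (Follow-up for Adverse Events) has staff follow an event "until the parent/subject provides a date of resolution for the AE", so the participant is accepted as a source there. For severe non-serious events, however, the follow-up telephone call goes to the parent, with no exception at age 18.

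**The concern.** Many adverse events are felt by the participant before anyone else can see them. The consenting procedure itself requires an explanation of this topic: "Potential risk of hypervitaminosis D (vitamin D poisoning) and its symptoms". If the one scripted question goes to the parent, a symptom that the adolescent has not mentioned at home is recorded only if the adolescent raises it unprompted. For an 18-year-old who attends alone, the rule taken literally produces no prompt at all.

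The later safety steps depend on events first being identified. These are the investigator's assessment of severity and relatedness (7.3), the 5-day IRB notice for related events of moderate severity and the annual report to the monitoring board (7.4), and the independent safety monitor's review (7.6). Passive reporting by the person taking the supplement is a weak base for them.

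**Working it through.** No formula applies, and the plan states no figure on this point. The check sets the relevant sections side by side.

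1. **Who is prompted.** Section 7.3 names the parent. None of the consent, visit, safety and follow-up sections in the available text directs an adverse event question to the participant.

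2. **Who is in the trial.** Ages 10 to 18, up to the day before the 19th birthday (4.1; 6.2 Screening). Those aged 18 give their own consent (4.3; 6.2; 11.2), and no section requires a parent at their visits.

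3. **Whether the protocol makes an age-18 exception elsewhere.** It does. The vitamin D and sunlight questionnaire carries the instruction "To be completed by parents unless subject is 18 years of age". The contact form and skin-type estimate have an equivalent exception, and the nutritional survey is self-completed at 18 (6.2, Baseline Assessments). The adverse event prompt in 7.3 and the call in 7.5 do not.

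4. **Whether minors are treated as able to report.** They are. Section 4.1 requires participants to understand the study procedures. In 6.2 they rate their own pubertal stage and may complete the activity survey, with parental help if 17 or younger. Asking them about symptoms is in keeping with this.

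5. **Whether another step supplies the question.** The schedule in 6.1 and the lists for the 3-month and final visits have no adverse event item. Medical history is taken at every visit. Its content, described only under Screening, covers measurements, demographics, education, smoking, medications and insurance, with no symptom question. Its content at follow-up is not described separately.

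6. **What does not depend on the parent.** Serum calcium is measured at 3 and 6 months (7.2), and abnormal laboratory findings count as adverse events (7.3). This covers a laboratory abnormality, not symptoms in general.

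7. **What happens to a volunteered symptom.** The recording rule in 7.3 covers all adverse events and does not restrict who reports them. A symptom that the participant mentions must be recorded.

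Steps 1 to 5 establish that active elicitation is specified from the parent alone. Steps 6 and 7 limit the consequence to symptoms that the parent does not know of and the participant does not volunteer.

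**The case against.** The strongest reply is that this is loose drafting. The protocol uses the parent as shorthand elsewhere: the consent points are listed as explained to parents or guardians although 18-year-olds sign for themselves, and parents are told to log each dose with no exception at 18. Staff may well ask the participant in practice. An operations manual is planned (10.2) and is not among the documents, and 10.3 provides for audits that cover adverse event reporting. All of this is fair, and it makes a deliberate decision to leave participants unasked unlikely. It does not supply the missing instruction, and the written rule is the one that staff and auditors would follow.

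Three stronger readings are tempting, and the documents do not support them.

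- A reader might infer that a participant's symptoms are recorded only when a parent knows of them. That confuses who is prompted with whose report counts: 7.3 orders all adverse events to be recorded, and 7.5 accepts information from the participant.
- A reader might put a head count on the 18-year-olds by spreading the planned enrollment of 229 evenly over the age range, and treat them all as having no informant. The documents give no age distribution and no parental attendance pattern, and an 18-year-old can report for himself or herself.
- A reader might infer that the higher doses will look safer than they are, or that a dose comparison of adverse events loses power. The same rule applies in all three masked arms, no true dose-related excess is established, and section 9.5 plans no between-arm test of adverse events.

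**Conclusion.** The point holds in a limited form. As written, the protocol specifies active elicitation from the parent only, with no direct question to the participant and no exception at 18. This is inconsistent with its own handling of other forms. The likely effect is under-ascertainment of symptoms unknown to the parent, under a rule common to all three masked arms; bias between doses is not shown.

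The size cannot be derived, because the documents give neither the number of participants aged 18 nor the fraction of symptoms that parents miss. The conclusion does not depend on either figure. It rests on two assumptions: that staff follow 7.3 as written, and that no instruction outside the available text, such as the operations manual, already directs the question to the participant. The efficacy analysis is unaffected. This is an inexpensive improvement to safety capture, not a flaw that undermines the trial.

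**What to change.** Replace the elicitation sentence in 7.3 with wording such as: *To elicit adverse events, the participant, and for participants under 18 years also the parent, will be prompted at each encounter to report any change since the last contact.*

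Align 7.5 so that the follow-up call for severe non-serious events goes to the participant when he or she is aged 18. Both sentences should refer to age at the time of the contact, since a participant can have a birthday during the six months.

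The cost is two edited sentences and a prompt on the case report form. Somewhat more minor events will be recorded. No visit, procedure or staff member is added, and no clinical rule changes.
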